Aim 3: To conduct preliminary analyses exploring whether emerging adults who receive the intervention demonstrate improvement in key symptom domains. Specifically, 40 youth will be randomized to either the integrated treatment or standard care. Primary outcomes will include substance abuse and PTSD. Secondary outcomes will include criminal justice involvement, adaptive functioning, and other mental health symptoms.

The results of the study will have a **significant impact on public health** by informing treatments for co-occurring SUD/PTSD among justice-involved transition age youth, a group at the highest risk for these problems. Demonstrating the efficacy of an integrated treatment approach will provide a valuable clinical tool for community-based therapists to employ in the context of existing evidence-based treatments. Further, should compelling indications of efficacy be found and safety and acceptability be established, these aims will position the research to advance to an appropriately powered randomized controlled trial.

A. SIGNIFICANCE

Prevalence and consequences of substance use problems among emerging adults. Transition age youth (i.e., emerging adults, ages 18-25) represent the age group with the **highest rates of initiation of substance use, increases in substance use, and progression of substance use into substance use disorders** (Chassin, Flora, & King, 2004; Delucchi, Matzger, & Weisner, 2008; SAMHSA, 2009). Substance use plays a significant role in many serious problems during this developmental period, including suicide (SAMHSA, 2010), automobile accidents (Hingson, Heeren, Winter, & Wechsler, 2005), and other lethal events. Emerging adults with SUDs also have increased rates of risky sexual behavior, increasing their chances of contracting HIV and other STDs (King, Nguyen, Kosterman, Bailey, & Hawkins, 2012). Further, SUDs significantly impede successful negotiation of important developmental tasks of this transitional age, leading to increased rates of unemployment and job instability and decreased college attendance (Bray et al., 2000; Mangione et al., 1999). Finally, emerging adults with SUDs represent a greatly underserved population, with a high likelihood of “slipping through the cracks” as they transition from child to adult substance use service providers ([name], Green, & Hoffman, 2009). **Thus, this group has a very high potential to present significant short- and long-term costs for individuals, families, and society.**

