The Trauma Assessment for Adults (TAA; Gray, Elhai, Owen, & Monroe, 2009) will be used to screen for exposure to traumatic events, as the diagnosis of PTSD or subthreshold PTSD is contingent upon the experience of a qualifying traumatic event. In addition, the TAA assesses current involvement in violent relationships and will be used to assess the exclusion criteria "currently in a domestic violence relationship."

The National Stressful Events Survey PTSD Short Scale (NSESP-SS) (Miller et al., 2013), a validated self-report measure of DSM-V PTSD symptoms, will be used to screen for PTSD. THE NSESP-SS is a 20-item measure including subscales for intrusion, avoidance, negative cognitive/mood alterations, and hyperarousal/reactivity. The reference period will be "since the crime event occurred" at the screening/BL assessment and "past month" for each subsequent assessment. It is likely that emerging adults with both clinical and sub-clinical levels of PTSD will benefit from this treatment; therefore, emerging adults will meet study criteria if they: (a) report an index trauma; (b) meet criteria for 2 of the 4 DSM-V PTSD symptom cluster and (d) have significant functional impairment (i.e., the recommendation for determining subthreshold PTSD using DSM-V criteria; McLaughlin et al., 2015). This instrument will be used at each of the assessments as well as once per week during the participant's scheduled sessions.

The Addiction Severity Index (ASI) (McLellan et al., 1988) is a structured interview that assesses demographic information as well as areas affected by substance use disorders: alcohol use, drug use, medical status, legal status, psychiatric, employment, gambling, cigarette smoking, and social functioning. Adequate interrater and test-retest reliability, and concurrent and discriminant validity, have been established (McLellan et al., 1985; Zanis et al., 1994). An abbreviated version will be administered at follow-up.

Timeline Follow-back (TLFB; Sobell et al., 1980) uses calendar prompts to elicit specific information about the frequency and intensity of substance use over time intervals with good test-retest reliability and validity (Sobell & Sobell, 1992). It will assess days and quantity of alcohol use and days of cocaine, opioid, benzodiazepine, marijuana or other drug use 3 months before treatment, every session throughout treatment, and since the last interview at follow-up.

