The Psychiatric Diagnostic Screening Questionnaire (PDSQ) (Zimmerman & Shereen, 2003) is a brief, psychometrically strong self-report scale that screens for the most common Axis I DSM-IV disorders encountered in outpatient settings. For the current study, modules for the following disorders will be used: 1) obsessive compulsive disorder; 2) panic disorder; 3) psychotic symptoms; 4) agoraphobia; 5) social phobia; 6) generalized anxiety disorder; 7) physical health problems; and 8) hypochondria.

The HIV Risk Behavior Scale (HRBS; Darke et al., 1991) assesses injection and sexual risk behaviors over time; it has adequate reliability and validity (Barry et al., 2008; Petry, 2001) and provides continuous summary scores. The HRBS will assess lifetime and past 3 months at baseline and the past 3 months at all other time points.

The Quality of Life Inventory (QOL; Frisch, et al., 1992) assesses satisfaction in 17 life areas (work, health, recreation, goals, etc). It has test-retest coefficients of .80-.91 and correlates with other measures of well-being (Frisch, et al., 1992); scores change in response to CM (Petry et al., 2007b).

The COPE Inventory (COPE; Carver, Scheier, & Weintraub, 1989) is a well validated measure of a broad range of coping responses that individuals use in response to stress. Five scales measure aspects of emotion-focused coping (e.g., seeking of emotional social support, positive reinterpretation, acceptance, denial, turning to religion); and three scales that measure less adaptive coping strategies (e.g., focusing on and venting of emotions, behavioral disengagement, mental disengagement).

The Center for Epidemiological Studies-Depressed Mood scale (CES-D; Radloff, 1977; Thomas et al., 2001) is a widely used, reliable and valid index for assessing depressive symptoms. This instrument will be used at each of the assessments as well as once per week during the participant's scheduled sessions.

The Self-Reported Offending Scale (SRO; Huizinga, 1991) was adapted from the Self-Reported Delinquency Scale (Elliott, Ageton, Huizinga, Knowles, & Canter, 1983) to be used for adult rather than juvenile offending (i.e., delinquency). The SRO will be used to assess the participant's involvement in delinquent acts during the past 90 days. The SRO includes a general delinquency scale as well as subscales that pertain to person offenses (e.g., assault) and property offenses (e.g., vandalism).

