The Service Utilization Form (SU; Rosenheck et al., 1995) evaluates drug abuse, medical, and mental health treatments received at the clinic and elsewhere. It inquires about services in the past 12 months at baseline and since the last interview at other points. It also collects information about societal costs related to drug abuse (e.g., unemployment, homelessness, criminal justice involvement). It contains similar items as the Treatment Services Review (McLellan et al., 1992) but is more extensive. An abbreviated version will be administered at follow-up.

Objective indicators of substance use will be assessed at each evaluation and during treatment. We will assess recent alcohol use (e.g., Alcosensor IV Alcometer, Intoximeters, St. Louis, MO) and cocaine, amphetamine, methamphetamine, opiate, benzodiazepine, and marijuana use (e.g., iCup, Brooklyn, NY) at BL, all follow-ups, and every treatment session.

Treatment Feasibility. Individual qualitative interviews will be conducted with each participant to assess treatment feasibility, acceptability, and burden as well as acceptability and burden of the research protocol.

Scale	Data	Baseline	Weekly during sessions	3 month follow-up	6 month follow-up
DSM-5 Criteria Checklist	Substance use disorder	X*			
Trauma Assessment for Adults	Exposure to traumatic events	X*		X	X
Urine Toxicology, Breathalyzers	Substance Use	X*	X	X	X
National Stressful Events Survey PTSD Short Scale	PTSD symptoms	X	X	X	X
National Opinion Research Center Diagnostic Screen	Pathological gambling	X*			
Structured Clinical Interview for DSM-5 PTSD Module	PTSD Diagnosis	X*			
Timeline Follow-back	Substance use	X	X	X	X
Addiction Severity Index	Substance use & related problems, demographics	X		X	X
Center for Epidemiological Studies-Depressed Mood scale	Depression symptoms	X	X	X	X
Psychiatric Diagnostic Screening Questionnaire	Co-occurring mental health problems	X		X	X
HIV Risk Behavior Scale	HIV Risk Behaviors	X		X	X
Service Utilization Form	Use of community services	X		X	X
Self-reported Offending (SRO)	Criminal behavior	X		X	X
Quality of Life (QoL)	Life satisfaction	X		X	X
COPE Inventory (COPE)	Coping skills	X		X	X
Qualitative Interview with Participants	Treatment acceptability			X	

*indicates measures that will be used to assess inclusion/exclusion criteria

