be assessed with HLM, coding patients as improved or not at each time point. The main analyses will focus on during treatment effects (baseline through follow-up) but long-term effects (baseline to 3-month post-treatment follow-up) will also be analyzed (see follow-up section).

The primary outcomes are substance use is longest duration of abstinence from illicit drug use and symptoms of PTSD (NSESP-SS), continuous variables that can be transformed if needed. The primary substance use outcome is longest duration of abstinence from substances (LDA), the main outcome variable in most CM trials and the variable most strongly associated with long-term abstinence (Higgins et al., 1994, 2000, 2003; Petry et al., 2005). Linear regression will evaluate group differences in LDA, with condition as the independent variable (along with any important covariates). If data cannot be normalized, nonparametric tests will be used. While LDA is the primary substance use outcome measure, it is affected by retention as missing samples break a string of abstinence (unless preceded and followed by negative samples, and an excused 'miss' is obtained due to documented illness, court appearances, etc. usually comprising <5% of missed samples). Proportion of negative samples, in contrast, is unaffected by missing samples. Thus, we will also analyze proportion of samples negative for substances as a secondary outcome using similar analyses.

Analyses will focus on the 10-week during treatment effects, but long-term effects will also be analyzed. These will involve logistic regressions to predict substance abstinence at the 3-month follow-up, with treatment group and any important baseline characteristics (e.g., baseline sample result) included as independent variables. HLM analyses for dichotomous measures will also be conducted to evaluate substance abstinence over time between treatments from baseline throughout the 3-month follow-up. Additional secondary drug use outcomes will investigate abstinence from all substances concurrently and from each of the other drugs independently. These analyses will parallel those outlined above.

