Effects of treatment on PTSD symptoms will be examined primarily using the weekly scores on the NSESP-SS. This is a continuous measure, with missing data likely. If no systematic differences in missing data are noted (the case in our prior studies), hierarchical linear models (HLM; Gibbons et al., 1993) using MIXREG (Hedeker, 1993) will analyze differences between groups over time. These analyses have advantages over repeated measures ANOVA as they estimate missing data via model parameter estimates and use real time, rather than scheduled time, of assessments. The model will include factors for group, time, and the interaction of group by time.

Secondary outcomes include delinquent behaviors (SRD), HIV risk behaviors (HRSB), adaptive functioning (SAS-SR), and depression (CES-D). Using the same HLM modeling described above, we will examine the impact of group, time, and group x time on each of these secondary outcomes to determine if the PE/CM treatment produces better outcomes than usual services.

Contingency Plan: If the intervention is not found to be feasible and/or produce symptom reduction, the candidate will work closely with mentors during Yr 5 to evaluate where positive outcomes are lacking and to refine the intervention using both quantitative and qualitative approaches. Assessment results will be evaluated to determine whether the intervention is equally effective across all areas targeted in treatment. If the intervention is found to be less effective in a specific area, modifications will be made to enhance the intervention in that area. Data will be examined to determine whether specific factors explain differential effects among participants. Input from participants will also be a critical source of information for improving the intervention.

PROTECTION OF HUMAN SUBJECTS

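### The primary PTSD scale (NSESP-SS) uses a since-event window at baseline and a past-month window afterwards, so change from baseline mixes a change of question with a change in symptoms

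*Combined protocol and SAP*

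**What the plan says.** Section C (Approach), Assessments, sets the NSESP-SS windows: "The reference period will be 'since the crime event occurred' at the screening/BL assessment and 'past month' for each subsequent assessment". It adds: "This instrument will be used at each of the assessments as well as once per week during the participant's scheduled sessions". The window of the weekly session forms is not stated separately; the natural reading is that they count as later assessments and use the past month.

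The Data Analysis Strategy, Aim 3, names the NSESP-SS as a primary outcome beside longest duration of abstinence. For all outcomes it says: "The main analyses will focus on during treatment effects (baseline through follow-up) but long-term effects (baseline to 3-month post-treatment follow-up) will also be analyzed". For PTSD it relies mainly on the weekly scores, uses actual rather than scheduled assessment times, and specifies: "The model will include factors for group, time, and the interaction of group by time". If data cannot be normalised, each patient is instead coded as improved or not at each time point. What improvement is measured against is not defined.

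The HIV risk scale is treated differently: "The HRBS will assess lifetime and past 3 months at baseline and the past 3 months at all other time points". That scale has a baseline score on the same window as its follow-up scores; the NSESP-SS does not. The only other PTSD measure at baseline, the SCID module, is diagnostic and is not repeated.

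**The concern.** For any trauma more than a month old, the since-event window contains the past month and more. A participant whose symptoms are stable could then score higher at baseline than later, only because the baseline question covers more time. An apparent fall would follow in both arms, with or without treatment.

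Three uses of the data are exposed: within-arm change from baseline, any time effect fitted with baseline included, and the fallback coding if improvement is judged against baseline. The Contingency Plan is triggered by a condition that names no comparator: "If the intervention is not found to be feasible and/or produce symptom reduction". If that is judged within the treated arm, a fall due to wording would count as symptom reduction.

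**Working it through.** The plan gives no SD, effect size or figure for this shift, so there is nothing of its own to reproduce. What follows expresses the consequences as multiples of d, the amount by which the longer window raises the baseline score.

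**Inputs from the protocol.** 20 per arm; weekly scores over 10 weeks in Group A and 10 to 12 weeks in Group B; follow-up at about 3 and 6 months post-baseline.

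**Assumptions.** Unit variances; later scores correlate rho = 0.6 with each other; baseline correlates r with each of them. A since-event baseline may track past-month scores less well, so r runs from 0.6 down to 0.3. Months 3 and 6 are weeks 13 and 26.

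**1. Simple change from baseline.** Expected change = true change − d in each arm. With no true change, the apparent fall is d.

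**2. Straight line with baseline as time 0.** The artefact is the slope fitted to an indicator that is 1 at baseline and 0 afterwards: slope = second element of (X′V⁻¹X)⁻¹X′V⁻¹e. When r = rho this equals ordinary least squares, so it can be checked by hand:
- Weeks 0 to 10: −5/110 = −0.04545 per week; × 10 gives a fall of 0.455d.
- Weeks 0, 13, 26: −13/338 = −0.03846 per week; × 26 gives a fall of 1.0d.

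For lower r, with the standard error (SE) of the group-by-time slope relative to r = 0.6:

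| Times in the line | r = 0.6 | r = 0.5 | r = 0.4 | r = 0.3 |
|---|---|---|---|---|
| Weeks 0–10, fall by week 10 | 0.455d | 0.339d | 0.270d | 0.225d |
| SE ratio | 1.000 | 1.042 | 1.065 | 1.081 |
| Weeks 0–10, 13, 26, fall by week 10 | 0.131d | 0.093d | 0.072d | 0.059d |
| SE ratio | 1.000 | 1.017 | 1.026 | 1.031 |
| Weeks 0, 13, 26, fall by week 26 | 1.000d | 0.923d | 0.857d | 0.800d |
| SE ratio | 1.000 | 1.109 | 1.195 | 1.265 |

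For the weeks 0–10 line with rho from 0.5 to 0.8 and r lower by 0.1 to 0.3, the fall ranges from 0.149d to 0.357d and the SE ratio from 1.035 to 1.106.

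**3. What that could look like in one arm of 20.** Suppose no true change and a baseline-to-follow-up correlation of 0.5. A paired t-test has noncentrality d/√(2(1 − 0.5)) × √20, with d in SD units: 1.118 for d = 0.25 and 2.236 for d = 0.5. The chance of a significant change (two-sided 5%) is 0.186 and 0.565, against 0.05 with matched windows.

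**4. The randomised contrast.** Both arms receive the same wording at the same visit, so d cancels when visit times match. In 20,000 simulated trials with d of 0.5 and 1.0 SD, the mean between-arm difference in change stayed within 0.003 of zero and type I error was about 5%.

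Times need not match. Take Group A scored at weeks 0 to 10, and Group B at baseline plus ten sessions spread evenly to week 12. Group B's times are 1.2 times Group A's, so its spurious slope is smaller by that factor. The false difference by week 10 is the Group A fall × (1 − 1/1.2), which is the fall divided by 6:
- r = 0.6: 0.455d/6 = 0.076d
- r = 0.5: 0.339d/6 = 0.056d
- r = 0.4: 0.270d/6 = 0.045d

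If d is positive, this works against Group B. With time as categories it disappears.

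**5. Baseline left out of the weekly model.** The indicator is never fitted. Bias and precision loss are both zero there, provided the weekly forms share one window.

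**The case against.** The strongest reply is that the plan tests efficacy between arms. A reader might take Aim 3's aim of "exploring whether emerging adults who receive the intervention demonstrate improvement in key symptom domains" as a pre-specified within-arm test. The next sentence of that aim randomises 40 youth to the integrated treatment or standard care, and the analysis section compares groups over time, so that reading is not supported. Nor can one infer that the mismatch makes the treatment look better than standard care: a common shift cancels, and the timing artefact, if d is positive, runs the other way. This stands, and it limits the harm. It does not justify the opposite claim that the randomised contrast is wholly safe, because the model uses actual times and treatment length can differ by arm.

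A reader might also cite the schedule of assessments, where "National Stressful Events Survey PTSD Short Scale" has one baseline mark, as proof that only one form is given. It is not proof: the HIV risk scale also has one baseline mark and uses two windows. The point rests on the windows stated under Assessments and on the absence of any past-month baseline form elsewhere.

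The PTSD paragraph puts the weekly scores first and may intend to leave baseline out. That is possible, but it is not stated, and the general text starts its analyses at baseline. Finally, size and direction are unknown; for a recent trauma the two windows nearly coincide. That also stands. Even so, with unmatched windows no within-arm change from baseline can be read as symptom change alone.

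**Conclusion.** The mismatch is real and concerns a primary outcome. Within-arm change from baseline, time effects that include baseline, and the improved-or-not fallback if judged against baseline cannot separate wording from symptoms. The direction is probably falsely favourable, but this is an inference: the documents give neither the size nor the sign of d.

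The false fall is d for simple change, 0.80d to 1.0d for a baseline/3/6-month line, and 0.22d to 0.45d for a line over weeks 0 to 10 at rho = 0.6. Precision loss is a few percent in the weekly model (4% to 8% at r = 0.5 to 0.3) but about 11% to 26% in the three-visit line at the same r, so it is not always small. These multiples depend on the straight-line form and the assumed correlations.

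The randomised group-by-time contrast is unbiased if time is categorical, or if timing and missingness match across arms. With real time, a straight line and 10 versus up to 12 weeks of treatment, an artefact of about 0.05d to 0.08d by week 10 is possible (r = 0.4 to 0.6). The documents do not support a claim that the main efficacy comparison is invalid. This is a cheap improvement.

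**What to change.** At baseline, also collect the NSESP-SS with the past-month window, as is already done in kind for the HIV risk scale. Use that score as the baseline in the outcome models and keep the since-event version for screening.

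For anyone already enrolled without a past-month baseline, use the since-event score only as a covariate, never as an outcome time point, and do not interpret within-arm change from it.

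In the same edit, state the window of the weekly forms, whether baseline enters the weekly model, and what improvement is judged against in the fallback and the Contingency Plan.

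The cost is one extra 20-item form at a 3-hour baseline visit, with no added patients or staff.

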Incarceration: This is a minimal risk study that recruits non-prisoner patients from substance abuse treatment programs. However, a portion of the study patients are likely to be incarcerated during the study period due to illegal activities that are common in this population. If a patient is incarcerated during study participation, all study procedures are suspended except the evaluations. In the ICF, patients indicate whether or not they would like the evaluation questionnaires sent to them in prison. The mailing delivered to the incarcerated patient only contains the evaluation questionnaires and a cover letter indicating the questionnaires are follow-up to a study the patient participated in at UConn Health. A stamped and addressed return envelope is also provided with the questionnaires. If the patient completes and returns the questionnaires for Month 3 and 6, they will receive \$25 in the form of a check. The patient will receive the check after their release from incarceration or they may designate a person to whom the check should be sent during their incarceration. The patient is notified in the ICF that their participation in this study while incarcerated will have no effect on their eligibility for parole.

Compensation: To compensate for their time, participants will be given a \$50 giftcard for the baseline interview and \$100 in their choice of a check or giftcard for each subsequent interview. Participants in the control group will be compensated \$5 (check or giftcards) for each urine sample they provide during the treatment phase (i.e., two samples per week for ten weeks). Participants who travel to UConn for their study visits will be provided with \$15 (check or giftcards) to cover the cost of travel (bus passes, gas, parking, etc). Participants may also earn up to \$45 for eligible referrals (\$15 each, up to 3 referrals).

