Random Assignment occurs after the BL evaluation. A computerized urn randomization procedure (Stout et al., 1994) will balance patients on gender and submission of a positive sample for any illicit drug (i.e., cocaine, amphetamine, methamphetamine, opiate, benzodiazepine, or marijuana) at baseline, because positive samples at treatment initiation are related to poor outcomes (Preston et al., 1998; Silverman et al., 1998; Stitzer et al., 2007). Prior to randomizing participants, up to 10 pilot participants will complete a pilot study consent form and study procedures described for Group B below, through month 3 follow-up, for the purpose of monitoring staff on study procedures prior to the randomized trial.

Group A (Standard care [SC]; n=20) patients will receive SC at the substance use clinic where they are seeking treatment. This treatment approach typically consists of group therapy sessions, including daily planning, 12-Step treatment, relapse prevention, coping and life skills training, and AIDS education. Groups are led by recovering individuals, nurses, and masters level counselors. Very few individual sessions are provided at these clinics, and then only in cases of emergencies (e.g., suicidality). These clinics rarely conduct breathalyzers or urine testing for illicit drug use. Any such testing will occur as it normally would, and study procedures will not

impact standard care in any way. If the participant is not already enrolled in SC at a substance use clinic, they will be provided with referrals to clinics convenient to their home.

Study urine samples will be collected twice weekly. Patients will receive a \$5 payment (check or gift cards) for each of 20 urine/breath sample submissions during weeks 1-10. In addition, they will be asked to complete the NSSEP-SS and the CES-D to assess PTSD symptoms and depression weekly. If patients cease attending groups, they will still be encouraged to attend these brief meetings for sample monitoring. To maintain consistency with standard care in these clinics, results from toxicology screens will not be discussed with providers.

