Group B (SC + PE/CM Treatment; n=20) patients will receive the same SC groups as Group A. If they are currently enrolled in substance use treatment, they will continue with that treatment. If not, they will be provided with referrals for substance use treatment in the community. In addition, they will participate in an integrated Contingency Management (CM) and Prolonged Exposure (PE) treatment protocol described subsequently. Either the PI ([name]) or [name], will serve as the study therapist for participants randomized to group B. For cases where [name] serves as the therapist, [name] will provide clinical supervision of study cases.

As in Group A, participants will undergo testing twice weekly with a breathalyzer and urine drug screen. In addition, during the first meeting of the week, participants will engage in both CM and PE components of treatment (described below). During the second meeting of the week, participants will engage in CM and a brief check-in on the components of PE that the participant is working on for homework that week but no new PE-related components will be introduced.

Contingency Management Component. Participants in Group B will participate in CM to target abstinence from substance use. In prize CM protocols, participants earn opportunities to draw cards from a prize bowl. The cards differ in prize value, ranging from \$0 to \$100 in value, and participants can earn increasing numbers of draws with consecutive performance. The variable reinforcement amount feature of prize CM distinguishes it from other reinforcement systems such as voucher CM. Participants will be allowed to draw from the prize bowl if their urine drug screen is negative for opiates, methadone, cocaine, amphetamines, methamphetamines, and marijuana (see additional information about marijuana use below) and their breath screen is negative for alcohol.

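### Participants are expected to be jailed and are still evaluated, but the Aim 3 analysis makes no allowance for time in custody and has no planned analysis of arrest or incarceration

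*Combined protocol and SAP*

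**What the plan says.** The Incarceration paragraph in section C (Approach), repeated under Adequacy of Protection Against Risks, expects a portion of participants to be jailed during the study because of illegal activity. It then states: "If a patient is incarcerated during study participation, all study procedures are suspended except the evaluations". Those who opted in at consent are mailed the questionnaires with a cover letter and return envelope. The mailing includes no urine or breath test. The paragraph on follow-up scheduling lists being in a controlled environment among the reasons why participants become unavailable.

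Under Assessments, the SRO covers the past 90 days, the HIV Risk Behavior Scale (HRBS) the past 3 months, and the Timeline Follow-back (TLFB) the time since the last interview. The Addiction Severity Index (ASI) includes legal status. Of the Service Utilization Form the protocol says: "It also collects information about societal costs related to drug abuse (e.g., unemployment, homelessness, criminal justice involvement". Both the ASI and the Service Utilization Form are abbreviated at follow-up.

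Aim 3 in Specific Aims reads: "Secondary outcomes will include criminal justice involvement, adaptive functioning, and other mental health symptoms". The Data Analysis Strategy lists: "Secondary outcomes include delinquent behaviors (SRD), HIV risk behaviors (HRSB), adaptive functioning (SAS-SR), and depression (CES-D", each modelled by group, time and their interaction. Long-term substance use is to be analysed by "logistic regressions to predict substance abstinence at the 3-month follow-up". Custody, days at risk and coding of jailed participants appear nowhere in the Data Analysis Strategy.

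**The concern.** A participant jailed for 60 of the 90 days has about 30 days in which to offend in the community, but the score is analysed as if it covered 90. This does not depend on the prison mailing: someone released before the visit and interviewed in the usual way has the same shortened exposure. If the treatment lowers incarceration, its participants have more time at liberty and can look worse on offending. If the treatment arm has more incarceration, it can look better.

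The justice data that would show this have no planned analysis, although Aim 3 names justice involvement as an outcome and the Innovation section promises to examine its impact on treatment outcome. For follow-up abstinence, custody leaves at most a self-report. With 20 per arm, an unstated coding choice for a few people could decide the direction of the comparison. The pilot's data are meant to support an application for a larger trial, so these estimates would be carried forward.

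**Working it through.** **Inputs from the documents.** "40 youth will be randomized to either the integrated treatment or standard care"; "Group A (Standard care [SC]; n=20" and "Group B (SC + PE/CM Treatment; n=20", so 20 per arm. The SRO window is 90 days. There are 20 scheduled samples over 10 weeks. No incarceration rate or duration, no power calculation and no expected effect is given, so there is no stated figure to reproduce.

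**Assumptions (mine).** The SRO score rises in proportion to days at liberty. Both arms offend equally per day at liberty, so the true ratio is 1.00. A share j of an arm is jailed for d of the 90 days. I take the measure abbreviated SRD in the analysis section to be the SRO described under Assessments.

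**Step 1: offending.** Expected score relative to full liberty = 1 − j × d/90. Ratio B/A = (1 − j_B × d/90) / (1 − j_A × d/90).

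| Jailed, A vs B | d = 45 | d = 60 | d = 90 |
|---|---|---|---|
| 15% vs 5% (3 vs 1 of 20) | 0.975/0.925 = 1.054 | 0.967/0.900 = 1.074 | 0.950/0.850 = 1.118 |
| 20% vs 5% (4 vs 1) | 0.975/0.900 = 1.083 | 0.967/0.867 = 1.115 | 0.950/0.800 = 1.188 |
| 25% vs 10% (5 vs 2) | 0.950/0.875 = 1.086 | 0.933/0.833 = 1.120 | 0.900/0.750 = 1.200 |

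Group B appears 5% to 20% worse with no true difference. A wider grid runs from 1.02 (10% vs 5% for 30 days: 88.5/87.0) to 1.29 (30% vs 10% for 90 days: 81/63). If the arms are swapped, the ratio inverts: 5% in A vs 20% in B for 60 days gives 0.867/0.967 = 0.90. With 20% jailed in both arms the ratio is 1.00, but both means are still lowered, by 20% if custody fills the window.

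**Step 2: follow-up abstinence.** Let p be abstinence among those at liberty, equal in both arms. Scoring jailed participants abstinent gives (1 − j)p + j; scoring them non-abstinent gives (1 − j)p; treating them as missing gives p. With p = 0.30 and 4/20 vs 2/20 jailed:

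| Coding of custody | A | B | B − A |
|---|---|---|---|
| Abstinent | 44% | 37% | −7 points |
| Non-abstinent | 24% | 27% | +3 points |
| Missing | 30% | 30% | 0 |

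Over p = 0.30 and 0.50 and jailed shares of 10% vs 5%, 20% vs 10% and 30% vs 10%, the artefact is −2.5 to −14 points under the first coding and +1.5 to +10 under the second. The sign depends on a choice that the plan does not make.

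**Step 3: longest duration of abstinence (LDA).** The plan says a missed sample breaks the run unless the miss is excused. A participant otherwise negative throughout but jailed in weeks 5 and 6 misses samples 9 to 12. The longest run is then 8 of 20 samples (4 weeks).

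**Step 4: named against analysed.** Aim 3 names justice involvement, other mental health symptoms and adaptive functioning. The analysis section carries forward delinquent behaviour, HIV risk, adaptive functioning and depression. Neither the ASI legal items nor the Service Utilization justice items appear in it.

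**The case against.** A reader might infer that incarceration scores as improvement throughout. The documents do not support that. No text codes a jailed participant as abstinent. The mailing needs an opt-in, the ASI is a structured interview and the TLFB uses calendar prompts, and the scheduling paragraph points towards unavailability, so many such follow-ups may simply be missing. On LDA, the primary substance outcome, unexcused custody counts against the participant (Step 3), and an excused miss at best leaves the run unbroken. The proportion of negative samples ignores missed samples.

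A reader might also infer that the Aim 3 justice outcome is not analysed at all. Self-reported offending is analysed, with a group-by-time model. What has no planned analysis is contact with the justice system itself.

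On size, every scenario in the table puts more custody in Group A, which is an assumption. The protocol attributes incarceration to illegal activity, so those jailed may offend above the average rate before arrest, which would shrink the artefact. It is also tempting to say that each jailed participant scored abstinent moves an arm by 5 points (1/20). That is the maximum; the expected shift is 5 × (1 − p), or 3.5 points at p = 0.30.

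Finally, the plan records reasons for failed interviews and makes its PTSD model conditional on a check for systematic missingness. Neither is a rule for custody, and neither covers jailed participants who are interviewed.

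These objections limit the claim. They leave standing the unadjusted 90-day score, the unspecified abstinence coding and the unanalysed justice items.

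**Conclusion.** The gap is real and should be closed, but it lies in the secondary and follow-up analyses of a 40-person pilot. Three parts hold. The 90-day offending score is lowered by time in custody, with no adjustment. Coding of follow-up abstinence in custody is unspecified. Justice involvement, named in Aim 3, is narrowed to self-reported delinquency without explanation.

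Between-arm bias arises only if custody differs by arm. Its size is unknown because no rate is given; under the three assumed pairs of rates it is about 5% to 20% on the offending ratio, and with equal rates it is zero. These figures rest on a score proportional to days at liberty and equal daily offending in the arms.

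A reader might conclude that custody should count as non-abstinent under the conservative rule in Data Quality Control. That rule settles disagreements between self-report and objective data. It says nothing about lack of opportunity to use, and Step 2 shows that this default can bias the comparison in the opposite direction.

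**What to change.** 1. Make criminal justice involvement an analysed Aim 3 secondary outcome, by arm, alongside the SRO: any arrest or incarceration, and days incarcerated. Confirm that the Service Utilization Form and ASI legal items needed for this are kept in the abbreviated follow-up forms. The protocol describes those items only in general terms, so their content should be checked.
2. Record days in a controlled environment on the TLFB calendar. Report the SRO and HRBS per day at liberty beside the raw result. Participants in custody for the whole window have no days at liberty and so no rate; report their number by arm, which is one reason to keep the raw result.
3. For follow-up abstinence, report the number in custody by arm and show the comparison with custody treated as missing, as abstinent and as non-abstinent. Do not default to non-abstinent.

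The cost is one extra day-count on an interview already given, a little more analysis, and possibly retaining a few items at follow-up. No new visit is needed. Incarceration for an offence before randomisation would otherwise count against an arm, so the offence date should be noted.
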